Accrual Ceiling:	N=700 Reconsent for Booster phase: Previously enrolled and vaccinated N=200
Study Population:	Healthy adults (18 to 35 years of age), residents in Ouelessebougou and surrounding villages, Mali
Accrual Period:	Approximately April 2018 to April 2019 (MAIN PHASE) Approximately April 2019 to March 2020 (BOOSTER PHASE)
Study Design:	A randomized double blind, placebo-controlled study to assess the safety, tolerability, immunogenicity and protective efficacy of 9×10^5 irradiated Plasmodium falciparum sporozoite (PfSPZ Vaccine) in healthy adults when given at 0, 8 and 16 weeks and at 0, 1 and 4 weeks. Participants will be randomized into four arms. At the completion of the follow up period in the first transmission season, the study will remain blinded and will assess the safety, tolerability, immunogenicity and protective efficacy of a 4 th vaccination (booster dose). Arms 1 and 2 will receive 9×10^5 PfSPZ Vaccine whereas Arm 3a and 3b will receive normal saline. The booster phase will evaluate efficacy in the subsequent transmission season.

Arm 1: (n=70) will receive 3 doses of PfSPZ Vaccine (9×10^5) via direct venous inoculation (DVI) at 0, 8, and 16 weeks. A 4th dose at 38 weeks post 3rd vaccination

Arm 2: (n=70) will receive 3 doses of PfSPZ Vaccine (9×10^5) via DVI at 0, 1 and 4 weeks. A 4th dose at 38 weeks post 3rd vaccination

Arm 3a: (n=35): Will be the control for Arm 1. Volunteers will receive 3 doses of placebo saline injection via DVI at 0, 8 and 16 weeks. A 4th dose at 38 weeks post 3rd injection

Arm 3b: (n=35): Will be the control for Arm 2. Volunteers will receive 3 doses of placebo saline injection via DVI at 0, 1 and 4 weeks. A 4th dose at 38 weeks post 3rd injection

- All injections will be administered by DVI.
- All volunteers will receive antimalarial treatment with artemether/lumefantrine (AL) 2 weeks prior to 3rd injection and 4th injection
- Participants will be monitored for safety, immunogenicity, malaria infection and disease during the follow-up period.

Study Duration:

MAIN PHASE

Start Date: Approximately April 2018

End Date: Approximately April 2019

BOOSTER PHASE

Start Date: Approximately April 2019

End Date: Approximately March 2020

Study Agent Description:

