3.1 Study Groups

Arm 1: (n=70) will receive 3 doses of PfSPZ Vaccine (9×10^5) via DVI at 0, 8, and 16 weeks in the main phase, booster dose at 38 weeks post 3rd vaccination.

Arm 2: (n=70) will receive 3 doses of PfSPZ Vaccine (9×10^5) via DVI at 0, 1 and 4 weeks in the main phase, booster dose at 38 weeks post 3rd vaccination.

Arm 3a: (n=35): Will be the control for Arm 1. Volunteers will receive 3 doses of placebo saline injection via DVI at 0, 8 and 16 weeks in the main phase, booster dose at 38 weeks post 3rd vaccination.

Arm 3b: (n=35): Will be the control for Arm 2. Volunteers will receive 3 doses of placebo saline injection via DVI at 0, 1 and 4 weeks in the main phase, booster dose at 38 weeks post 3rd vaccination.

All injections will be administered by DVI. All volunteers will receive antimalarial treatment with artemether/lumefantrine (AL) two weeks prior to 3rd injection. Post 3rd injection, participants will be followed through the rainy transmission season, approximately six months. Participants will be monitored for safety, immunogenicity, malaria infection and disease during the follow-up period.

Participants enrolled in the booster phase of the study, at the end of the prior transmission season, will also receive antimalaria treatment with artemether/lumefantrine (AL) at least two weeks prior to booster injection (4th injection overall). Post 4th injection, participants will be followed through the rainy transmission season, approximately six months. Participants will be monitored for safety, immunogenicity, malaria infection and disease during the follow-up period.

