6.3 Inclusion Criteria in the main phase and booster phase

Subjects must fulfill all the following criteria to be eligible for the study:

1. Age ≥ 18 and ≤ 35 years (For booster phase, age ≥ 18 and ≤ 37 years)
2. Able to provide proof of identity to the satisfaction of the study clinician completing the enrollment process
3. In good general health and without clinically significant medical history
4. Willing to have blood samples stored for future research
5. Available for the duration of the study
6. Females of childbearing potential must be willing to use reliable contraception (as defined below) from 21 days prior to Study Day 1 to 28 days after 3rd vaccination. (For the booster phase, from 21 days prior to the booster vaccination to 28 days post booster vaccination).
 - Reliable methods of birth control include:
 - **one** of the following: confirmed pharmacologic contraceptives (parenteral) delivery; intrauterine or implantable device. **OR**
 - **two** of the following: a documented oral or transdermal or vaginal ring contraceptives; **PLUS** condoms with spermicide or diaphragm with spermicide.
 - **Note-** Coartem (artemether specifically) may reduce the effectiveness of systemic hormonal contraceptives, therefore additional barrier methods such as condoms must also be used during the 3 days of Coartem dosing.

- Women who are not able to get pregnant will also be required to report date of last menstrual period, history of surgical sterility (i.e. tubal ligation, hysterectomy) or premature ovarian insufficiency (POI), and will have urine or serum pregnancy test performed per protocol.
7. Enrolled in protocol # 18-I-N084 and are enrolled in the active follow up phase of the study (For the booster phase only)
 8. Malaria comprehension exam completed, passed (a score of $\geq 80\%$ or per investigator's discretion) and reviewed prior to enrollment

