7 STUDY SCHEDULE

7.1 Screening

The purpose of the screening visit is to determine subject eligibility for study participation. Screening procedures include the informed consent process, Malaria Comprehension Exam, laboratory assessments (completed within 56 days of receipt of first and fourth vaccination) and clinical assessments. Screening activities can occur over multiple visits if necessary, including the day of enrollment.

In the event that a chronic illness and/or HIV, HBV, or HCV is discovered during the course of screening, long-term treatment and care will not be reimbursed by the study, but referral for continuing care can be provided to subjects.

Per national requirements for reporting communicable diseases, confirmed positive test results for HIV, HBV, and HCV will be reported to the local health department according to applicable laws and appropriate medical referrals initiated.

The following actions must be completed as part of the screening process for all subjects within the 56 days prior to first and fourth vaccination:

- Explain the study and informed consent document to the subject (For the booster phase, informed consent can be signed within 90 days prior to the 4th vaccination).
- Ensure the subject has acknowledged consent by signing or fingerprinting the informed consent document. Ensure that the subject receives a signed copy of the informed consent.
- Ensure the subject has correctly answered $\geq 80\%$ of the questions (see **Section 14.2.2**) on the Malaria Comprehension Exam.
- Elicit a complete medical history, including menstrual and contraceptive history and/or history of surgical sterility for females, and medication use.
- Confirm that females of childbearing potential are willing to use reliable contraception from at least the period from screening through 28 days after the third vaccination in the main phase. For the booster phase, use of reliable contraception should be at least 21 days prior to vaccination up to 28 days after the fourth vaccination.
- Administer a complete physical examination, including vital signs (height, weight, blood pressure, temperature, and heart rate).
- Complete HIV pre- and post-test counseling as indicated, including follow-up contact with subject to report the results and referral for appropriate medical care if indicated.

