7.2 Assignment of Groups

Enrollment **in the main phase** occurs with collection of baseline study samples on study Day -14. Randomization will occur prior to enrollment, prior to or on study Day -14. Randomization of the subjects in Arm 1 and 3a will occur first as these subjects will be enrolled first. Randomization of Arm 2 and 3b will occur together later prior to enrollment. If a subject was randomized into group 1 or 3a but was not vaccinated, they may be randomized into groups 2 and 3b if still eligible.

If a subject withdraws from the study after randomization, they can be replaced by another subject at random if withdrawal happens prior to receipt of first vaccination. Once a subject has received their first vaccination, they cannot be replaced.

For the booster phase, enrollment will occur at the receipt of the first dose of artemether/lumefantrine prior to vaccination. Enrolled subjects cannot be replaced.

During the study, the list linking randomization numbers to study product (PfSPZ Vaccine or control) will be made available only to the study statistician and associated team members, pharmacy team/syringe preparers (at the start of the study), independent safety monitor (if needed to review as outlined in **Section 11.15.2**), and DSMB chair (if needed for closed session unblinded review). On vaccination days, the vaccines associated with each randomization number will be obtained from the pharmacist.

To ensure proper identification of study subjects, following subject enrollment all subjects will receive an identification card with their photo on it to present at the clinic with each study visit.

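### Booster-phase contraception is timed from dose 4, so the required lead before pre-emptive artemether/lumefantrine, the first study drug of the phase, is only 4 days (range -3 to 6)

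*Combined protocol and SAP*

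**What the plan says.** Section 6.3 item 6 sets the booster-phase requirement: "For the booster phase, from 21 days prior to the booster vaccination to 28 days post booster vaccination". Section 7.1 repeats it with the same reference point: "use of reliable contraception should be at least 21 days prior to vaccination up to 28 days after the fourth vaccination". The words at least in 7.1 allow an earlier start, but neither section requires one.

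The main-phase rule in 6.3 runs "from 21 days prior to Study Day 1 to 28 days after 3rd vaccination". Study Day 1 is dose 1, the first study product of that phase.

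In the booster phase AL comes before the vaccine. Section 7.2 states that "enrollment will occur at the receipt of the first dose of artemether/lumefantrine prior to vaccination". On timing, the Protocol Summary says "All volunteers will receive antimalarial treatment with artemether/lumefantrine (AL) 2 weeks prior to 3rd injection and 4th injection", and Section 3.1 says booster participants "will also receive antimalaria treatment with artemether/lumefantrine (AL) at least two weeks prior to booster injection". Both Appendix A booster tables put AL at visit 3, Day -17, window -7/+2.

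The protocol has several safeguards:
- Section 15.7 requires pregnancy tests at screening and before AL, a serum test when the history suggests possible conception, counseling at visits, and exclusion of women planning pregnancy.
- The note in 6.3 adds that "additional barrier methods such as condoms must also be used during the 3 days of Coartem dosing".

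**The concern.** A contraception lead protects against a conception too recent for a pregnancy test to show. It should therefore be counted from the first product that carries a fetal concern. In the booster phase that product is AL, and the rule counts from an event about two and a half weeks later.

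Pre-emptive AL goes to every arm (Section 5.4.4), and no positive smear is needed. An uninfected woman has no treatment benefit to set against a fetal risk. Section 6.5 calls AL category C, for use in pregnancy only where benefit justifies the risk, and Section 15.7 gives quinine for uncomplicated malaria in the first trimester. A woman who conceived shortly before the AL visit could test negative, receive AL in very early pregnancy, and still have met the start date in 6.3 and 7.1.

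Some women may also be starting a method afresh. The main-phase requirement ends 28 days after dose 3, and dose 4 is 38 weeks (266 days) after dose 3. Nominally, 266 - 28 - 21 = 217 days pass with no stated contraception requirement.

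**Working it through.** **Inputs**
- Booster contraception starts 21 days before dose 4 (6.3, 7.1).
- AL is at Day -17, window -7/+2; dose 4 is at Day 0, window -7/+14; booster screening is at Day -28, window -14/+21 (Appendix A, both booster tables).
- AL is a 3-day course (6.3 note).
- Main-phase contraception starts 21 days before Study Day 1 (6.3).

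**Reproducing the schedule**
- Days from AL to dose 4: 379 - 362 = 17 (Arms 1/3a) and 295 - 278 = 17 (Arms 2/3b), matching Day -17.
- Study Day 1 is dose 1: 1 + 112 + 182 = 295 and 1 + 28 + 182 = 211, the main-phase final visits given in Section 4.4.
- AL window: -17 - 7 = -24 and -17 + 2 = -15.

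**Required lead before AL** = 21 minus the days from AL to dose 4, with dose 4 on its nominal day

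| AL day | Lead (days) |
|---|---|
| -24 (earliest) | 21 - 24 = -3 |
| -17 (nominal) | 21 - 17 = 4 |
| -15 (latest) | 21 - 15 = 6 |

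At the earliest AL visit the course covers Days -24 to -22 and ends before Day -21, when contraception is first required. At the Protocol Summary's two weeks exactly, the lead would be 21 - 14 = 7 days.

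**Comparison.** The like-for-like main-phase figure is 21 days before the first study product (dose 1), against 4 days in the booster phase.

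**Illustration, on an assumption not in the documents.** Suppose a test misses conceptions of the last 10 to 14 days. The days of that period outside required contraception are then:
- nominal AL: 10 - 4 = 6 to 14 - 4 = 10;
- latest AL: 10 - 6 = 4 to 14 - 6 = 8;
- earliest AL: all 10 to 14;
- main phase, before dose 1: none, since 21 exceeds 14.

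**Moving the dose 4 window as well.** If the AL and dose 4 windows ran independently, which the documents do not state, the lead would span 21 - (24 + 14) = -17 to 21 - (15 - 7) = 13 days. Enforcing a gap of at least two weeks makes the upper end 21 - 14 = 7.

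**The case against.** The strongest reply is that both phases apply one rule: 21 days before the first vaccination of the phase. The first reason 6.5 gives for excluding pregnant women is that the vaccine's fetal effects are unknown, and no section sets a required lead before AL.

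That stands, and it rules out a tempting stronger reading. With AL 14 days before dose 3, the main-phase interval from required contraception to AL works out at 21 + 28 - 14 = 35 days (Arms 2/3b) or 21 + 112 - 14 = 119 days (Arms 1/3a). A reader might infer that the booster phase departs from a main-phase AL standard. The documents do not support this. Those intervals arise only because AL was given after dose 1. The supplied text has no main-phase visit table to confirm the AL day, and 7.1 words the main-phase start differently, as at least from screening.

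A reader might also take -17 days as the worst case. It rests on independent windows. In addition, a woman who starts 21 days before the planned date does not lose that lead when dose 4 is deferred.

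The safeguards are substantial. Appendix A appears to place counseling from Day -28, 11 days before nominal AL, and pregnancy tests at screening and at the AL visit. The barrier rule means that even the -3 case is not AL dosing with no contraceptive rule in force. AL is a licensed product, which 15.7 itself uses in the second and third trimesters.

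The objection does not remove the gap. A history-triggered test depends on disclosure and has the same blind period. Barrier methods on the AL days do nothing about a conception a week earlier. Excluding women who plan pregnancy does not prevent unplanned conception.

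**Conclusion.** The point holds as a participant-safety improvement of low to moderate priority. The required lead before AL is 4 days at the nominal schedule and -3 to 6 days across the AL window, given dose 4 on its nominal day. This compares with 21 days before the first study product in the main phase. These figures follow directly from 6.3, 7.1 and Appendix A.

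The residual risk is an unplanned conception, not suggested by history and too recent to detect, despite recent counseling. It is small, and its size cannot be computed: the documents give neither the number of women nor their contraceptive use, and the 10-to-14-day blind period is an assumption. Endpoints, power and analysis are unaffected.

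**What to change.** In 6.3 item 6 and 7.1, reword the booster requirement to run *from at least 21 days before the first AL dose to 28 days after the booster vaccination*. State that booster consent and contraception counseling are done by that start, and that AL is scheduled no sooner than 21 days after it. The 21 days is the protocol's own lead before the first main-phase product.

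The start day is then:
- 17 + 21 = Day -38 for nominal AL;
- 15 + 21 = Day -36 for the latest AL;
- 24 + 21 = Day -45 for the earliest AL.

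Days -38 and -36 lie inside the booster screening window (-28 - 14 = Day -42 to -28 + 21 = Day -7). Day -45 is 3 days before that window opens, so AL at its earliest would need consent and counseling ahead of the screening visit, or a later AL date. Section 7.1 leaves room: "informed consent can be signed within 90 days prior to the 4th vaccination".

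Tie the rule to AL and not to a visit. Starting at screening would give 28 - 17 = 11 days before nominal AL but only 28 - 24 = 4 before the earliest, and the screening window extends past AL. A rule of merely starting before AL would allow a one-day lead.

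The cost is 38 - 21 = 17 more days of required contraception at nominal AL (15 to 24 across the AL window). Consent and counseling, which appear to sit at Day -28, would move about 38 - 28 = 10 days earlier for nominal AL and 45 - 28 = 17 for the earliest. Women already using an implant, intrauterine device or injectable keep their method.

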6.4 Exclusion Criteria in the main phase and booster phase

A subject will be excluded from participating in the trial if any one of the following criteria is fulfilled:

1. Pregnancy, as determined by a positive urine or serum human chorionic gonadotropin (β -hCG) test (if female)
NOTE: Pregnancy is also a criterion for discontinuation of any further dosing or non-safety related interventions for that subject.
2. Currently breast-feeding (if female)
3. Behavioral, cognitive, or psychiatric disease that in the opinion of the investigator affects the ability of the participant to understand and comply with the study protocol
4. Hemoglobin (Hb), WBC, absolute neutrophils, and platelets outside the local laboratory-defined limits of normal (subjects may be included at the investigator's discretion for 'not clinically significant' values)
5. Alanine transaminase (ALT) or creatinine (Cr) level above the local laboratory-defined upper limit of normal (subjects may be included at the investigator's discretion for 'not clinically significant' values)
6. Infected with human immunodeficiency virus (HIV), hepatitis C virus (HCV), or hepatitis B (HBV) (For the booster phase: re-testing NOT required for enrollment unless clinically indicated)
7. Known or documented sickle cell disease by history (Note: known sickle cell trait is NOT exclusionary)
8. Clinically significant abnormal electrocardiogram (ECG) such as abnormal QTc. (For the booster phase: re-testing NOT required for enrollment unless clinically indicated)
9. Evidence of clinically significant neurologic, cardiac, pulmonary, hepatic, endocrine, rheumatologic, autoimmune, hematological, oncologic, or renal disease by history, physical examination, and/or laboratory studies including urinalysis
10. History of receiving any investigational product within the past 30 days
11. Participation or planned participation in a clinical trial with an investigational product prior to completion of the follow-up visit 28 days following last vaccination OR planned participation in an investigational vaccine study until the last required protocol visit
12. Medical, occupational, or family problems as a result of alcohol or illicit drug use during the past 12 months
13. History of a severe allergic reaction (Grade 3 or higher or per PI discretion) or anaphylaxis

14. Severe asthma (defined as asthma that is unstable or required emergent care, urgent care, hospitalization, or intubation during the past two years, or that has required the use of oral or parenteral corticosteroids at any time during the past two years)
15. Pre-existing autoimmune or antibody-mediated diseases including but not limited to: systemic lupus erythematosus, rheumatoid arthritis, multiple sclerosis, Sjögren's syndrome, or autoimmune thrombocytopenia
16. Known immunodeficiency syndrome (For the booster phase: re-assessment NOT required for enrollment)
17. Known asplenia or functional asplenia (For the booster phase: re-assessment NOT required for enrollment)
18. Use of:
 - Chronic (≥ 14 days) oral or IV corticosteroids (excluding topical or nasal) at immunosuppressive doses (i.e., prednisone >10 mg/day) or immunosuppressive drugs within 30 days of vaccination
 - Artemether/lumefantrine within 14 days of vaccination **unless** it has been prescribed by the study investigator as part of study procedures
 - Other antimalarials or systemic antibiotics with known antimalarial activity within 5 drug half-lives prior to the first vaccine (such as artemether, sulfadoxine-pyrimethamine, trimethoprim-sulfamethoxazole, doxycycline, tetracycline, clindamycin, erythromycin, ciprofloxacin, other fluoroquinolones or azithromycin)
19. Receipt of a live vaccine within the past four weeks or a killed vaccine within the past two weeks prior to Vaccination #1 and every subsequent vaccination day
20. Receipt of immunoglobulins and/or blood products within the past six months
21. Previous receipt of an investigational malaria vaccine in the last five years (For booster phase: NOT required for enrollment)
22. Known allergies or other contraindications against Coartem
23. Other condition(s) that, in the opinion of the investigator, would jeopardize the safety or rights of a participant participating in the trial, interfere with the evaluation of the study objectives, or would render the subject unable to comply with the protocol

6.5 Justification for the Exclusion of Pregnant Women

This study will not enroll pregnant and/or breastfeeding women since the effects of PfSPZ Vaccine on the developing human fetus are unknown.

Artemether/lumefantrine is considered a category C medication, there are no adequate studies in pregnant women hence only recommended for use if the potential benefit justifies the potential risk to the fetus. However, if a woman becomes pregnant after enrollment she may continue in the study for safety follow up, malaria infection evaluation and reduced vaccine immunogenicity assays as described in **Appendix A** and as outlined in **Section 15.7**.

6.6 Justification for Exclusion of Children

Children are excluded from this study because there is insufficient data on dosing or adverse events available in children at the PfSPZ Vaccine doses proposed to be used in this study.

Studies evaluating the safety, tolerability and immunogenicity of various doses of PfSPZ Vaccine are ongoing.

7 STUDY SCHEDULE

7.1 Screening

The purpose of the screening visit is to determine subject eligibility for study participation. Screening procedures include the informed consent process, Malaria Comprehension Exam, laboratory assessments (completed within 56 days of receipt of first and fourth vaccination) and clinical assessments. Screening activities can occur over multiple visits if necessary, including the day of enrollment.

In the event that a chronic illness and/or HIV, HBV, or HCV is discovered during the course of screening, long-term treatment and care will not be reimbursed by the study, but referral for continuing care can be provided to subjects.

Per national requirements for reporting communicable diseases, confirmed positive test results for HIV, HBV, and HCV will be reported to the local health department according to applicable laws and appropriate medical referrals initiated.

The following actions must be completed as part of the screening process for all subjects within the 56 days prior to first and fourth vaccination:

- Explain the study and informed consent document to the subject (For the booster phase, informed consent can be signed within 90 days prior to the 4th vaccination).
- Ensure the subject has acknowledged consent by signing or fingerprinting the informed consent document. Ensure that the subject receives a signed copy of the informed consent.
- Ensure the subject has correctly answered $\geq 80\%$ of the questions (see **Section 14.2.2**) on the Malaria Comprehension Exam.
- Elicit a complete medical history, including menstrual and contraceptive history and/or history of surgical sterility for females, and medication use.
- Confirm that females of childbearing potential are willing to use reliable contraception from at least the period from screening through 28 days after the third vaccination in the main phase. For the booster phase, use of reliable contraception should be at least 21 days prior to vaccination up to 28 days after the fourth vaccination.
- Administer a complete physical examination, including vital signs (height, weight, blood pressure, temperature, and heart rate).
- Complete HIV pre- and post-test counseling as indicated, including follow-up contact with subject to report the results and referral for appropriate medical care if indicated.
- Obtain approximately 10 mL of blood for complete blood count (CBC) with differential and platelet count, ALT, creatinine (Cr), hepatitis B testing, hepatitis C testing, HIV testing, hemoglobinopathy testing (For the booster phase: HIV, hepatitis B, and hepatitis C testing will **only** be repeated if clinically indicated; hemoglobinopathy testing will **not** be repeated).
- Obtain urine (or serum) for pregnancy testing (for females) and urinalysis/urine dipstick for protein and blood.
- Obtain a 12-lead ECG (For booster screening: an ECG will **only** be repeated if clinically indicated).

Sickle cell testing will be completed retrospectively. History of known sickle cell disease is an exclusion at the time of enrollment. Discovery of sickle cell disease (HbSS) on subsequent laboratory testing will not result in the subject being withdrawn from the study.

Final eligibility will be determined at this point. The subject may be excluded by any of the above procedures if they meet the exclusion criteria. Acceptable ranges for hematological and biochemistry parameters defined for this study are given in **Appendix B**. (Note: parasitemia is not an exclusion criterion.)

If an abnormal finding is determined to be clinically significant, the subject will be informed, a referral letter will be issued, and the subject will be guided as to where to present for further investigation and medical care. Treatment for minor ailments may be provided by study clinicians at the study site. Decisions to exclude the subject from enrollment in the trial or to withdraw the subject from the trial will be at the discretion of the investigator.

